### 14.2 Adverse Events of Special Interest

A specific concern in treatment with botulinum toxin products is the potential for local and distant spread of toxin effect, a unique set of safety concerns related to use of botulinum toxin drug products (draft guidance for industry *Upper Facial Lines: Developing Botulinum Toxin Drug Products*). Therefore, subjects will be instructed and educated on possible warning signs and precautions and on rare AESIs through the Subject Information Sheet (SIS). Safety data related to this specific potential effect should be obtained through directed query at each study visit and if an AESI (as listed below) is reported, a targeted physical examination should be conducted to evaluate for signs and symptoms of local and distant spread of toxin effect. AESI assessment and documentation is mandatory based upon the event term. An AESI must also be reported even if e.g., the duration of the event is considered unusual for an AESI or if the event is considered as being not related to the study drug. AESIs potentially suggestive of distant spread of toxin include:

accommodation disorder	dyspnea	Paresis
areflexia	extraocular muscle paresis	peripheral nerve palsy
aspiration	eyelid function disorder	peripheral paralysis
blurred vision	eyelid ptosis	pelvic floor muscle
botulism	facial palsy	weakness
bradycardia	facial paresis	pneumonia aspiration
bulbar palsy	fourth cranial nerve	pupillary reflex impaired
constipation	paresis	quadripareisis
cranial nerve palsies	hemiparesis	respiratory arrest
cranial nerve paresis	hypoglossal nerve paresis	respiratory depression
cranial nerve paralysis	hyporeflexia	respiratory failure
diaphragmatic paralysis	hypotonia	speech disorder
diplopia	monoparesis	third cranial nerve paresis
dry mouth	muscular weakness	trigeminal nerve paresis
dysarthria	paralysis	urinary retention
dysphagia	paralysis flaccid	vocal cord paralysis
dysphonia	paralytic ileus	vocal cord paresis
	paraparesis	

The first AESI questioning will be undertaken (in accordance with the AESI Manual) prior to treatment, in order to obtain a full Baseline status of any concomitant diseases. If an AESI is reported, a targeted physical examination of the relevant area must be conducted.

### 14.3 Serious Adverse Events

An SAE is defined as an untoward medical occurrence that at any dose meets one or more of the following criteria:

- Results in death.
- Is life threatening – defined as an event in which the subject was, in the judgment of the investigator, at risk of death at the time of the event; it does not refer to an event that hypothetically might have caused death had it been more severe.
- Requires subject hospitalization or results in prolongation of existing hospitalization.
- Results in persistent or significant disability/incapacity.
- Is a congenital anomaly/birth defect.
- Is an important medical event.

Note: Medical or scientific judgment should be exercised in deciding whether reporting is appropriate in other situations, such as important medical events that may not be immediately life threatening or result in death or require hospitalization but may jeopardize the subject or may require medical or surgical intervention to prevent one of the other outcomes listed in the

definitions above. Examples of such events are: invasive or malignant cancers, intensive treatment in an emergency room or at home for allergic bronchospasm, blood dyscrasias, or convulsions that do not result in hospitalization, or development of drug dependence or drug abuse. Hospitalization is defined as at least one overnight stay. Pre-planned hospitalizations (known already prior to signing the ICF) will not be considered an SAE, unless any of above criteria are fulfilled over the course of the hospitalization due to unplanned complications.

#### **14.4 Treatment-Emergent Adverse Events (TEAEs)**

A TEAE is defined as any event not present prior to the initiation of the treatment, or any event already present that worsens in terms of severity, duration, or frequency following exposure to the treatment.

#### **14.5 Evaluation of AEs, AESIs, SAEs, TEAEs**

##### **14.5.1 Assessment of Causality**

The investigator is obliged to assess the relationship between the IMP as well as study procedure and the occurrence of each AE/AESI/SAE. This relationship will be classed as not related, unlikely, possibly, probably or definitely related as follows:

- Not related (both circumstances must be met):
  - Is due to underlying or concurrent illness, complications, concurrent treatments, or effects of concurrent drugs.
  - Is not associated with the IMP or study procedure (i.e., does not follow a reasonable temporal relationship to the administration of IMP or has a much more likely alternative etiology).
- Unlikely related (either one or both circumstances are met):
  - Has little or no temporal relationship to the IMP or study procedure.
  - A more likely alternative etiology exists.
- Possibly related (both circumstances must be met):
  - Follows a reasonable temporal relationship to the administration of IMP.
  - An alternative etiology is equally or less likely compared to the potential relationship to the IMP or study procedure.
- Probably related (both circumstances must be met):
  - Follows a reasonable temporal relationship to the administration of IMP, which may include but is not limited to the following:
    - Reappearance of a similar reaction upon re-administration (positive re-challenge).
    - Positive results in a drug sensitivity test (skin test, etc.).
    - Toxic level of the IMP as evidenced by measurement of the IMP concentrations in the blood or other bodily fluid.

- Another etiology is unlikely or significantly less likely
- Definitely related:
  - Has clear and undoubted relationship to the administration of IMP.

The investigator will use his/her clinical judgment to determine the relationship. Alternative causes, such as natural history of the underlying diseases, concomitant therapy, other risk factors, and the temporal relationship of the event to IMP administration will be considered and investigated. The investigator will also consult the IB in the determination of his/her assessment.

For the purpose of expedited regulatory reporting, events assessed as possibly, probably, or definitely related to IMP or study procedure will be considered as drug related.

#### **14.5.2 Assessment of Severity**

The following definitions for rating severity will be used:

- Mild:
  - The AE is easily tolerated and does not interfere with daily activity.
- Moderate:
  - The AE interferes with daily activity but the subject is still able to function.
- Severe:
  - The AE is incapacitating and/or requires medical intervention.

#### **14.5.3 Outcome**

The outcome options that can be utilized include:

- Ongoing
- Resolved
- Resolved with Sequelae
- Death
- Unknown

#### **14.5.4 Action Taken with Study Drug**

Action taken with study drug includes:

- None
- Discontinued

## 14.6 Adverse Event Monitoring and Assessment

Subjects will be monitored for AEs throughout the study from signing the ICF until the End of Study visit. Should an SAE occur after the End of Study visit, which is considered as at least possibly related to study drug or procedure, such events should always be reported to Croma or its representative, even after the end of the study. Such events would generally not be entered into the clinical database but will be entered into the safety database.

Subjects will be questioned concerning their well-being at all study visits from Screening through to the End of Study visit. Questions for evaluation of AEs will be posed in a non-leading manner, so as not to bias the response. In addition to questioning at specific time points, subjects will be encouraged to spontaneously report any AEs, AESIs, or SAEs. In addition, as per [Section 14.2](#), AESIs will be questioned in an active manner. Any subject with an AE, AESI, SAE or clinically significant abnormal test result will be evaluated by the investigator and will be treated and/or followed up as per local clinical practice. A physician, either at the investigative site or at a nearby hospital emergency room, will administer treatment for any SAEs. Where appropriate, medical tests and examinations may be performed to ensure that an AE has fully resolved. AEs, AESIs, and SAEs ongoing at End of Study will be followed up until the event is resolved or stable. Adverse events will be coded using the current version of the Medical Dictionary for Regulatory Activities (MedDRA). Whenever possible, a specific disease or syndrome, rather than individual associated signs and symptoms, should be identified by the investigator and recorded on the eCRF. However, if an observed or reported sign or symptom is not considered a component of a specific disease or syndrome by the investigator, it should be recorded as a separate AE on the eCRF.

When documenting AEs, standard medical terminology should be used in order to avoid the use of vague, ambiguous, or colloquial expressions (see [Section 14.1](#)). Each AE will be evaluated by the investigator for:

- Seriousness, as defined in [Section 14.3](#).
- Causal relationship to IMP exposure, as defined in [Section 14.5.1](#).
- Causal relationship to procedure, as defined in [Section 14.5.1](#).
- Severity, as defined in [Section 14.5.2](#).
- Outcome, as defined in [Section 14.5.3](#).
- Action taken with study drug, as defined in [Section 14.5.4](#).

If the severity rating for an ongoing AE worsens before the event resolves, the AE will be reported in an additional row in the AE log (or additional AE page) with complete information (i.e., start and stop date, severity, relationship, outcome, etc.).

#### **14.6.1 Reporting Serious Adverse Events and Adverse Events of Special Interest**

All SAEs and AESIs for all subjects occurring from the time of informed consent until the End of Study visit must be reported to Croma or their representative **within 24 hours** of the knowledge of the occurrence. If considered at least possibly related to study treatment, SAEs observed after the End of Study visit must also be reported.

Paper SAE/AESI forms should be completed at the site and emailed or faxed to the [REDACTED] **within 24 hours** of awareness of the event:

*The preferred way of submitting safety reports is via email; fax numbers are provided for backup.*

If a report is sent via email the completed and signed SAE/AESI or Pregnancy report form must be attached to the email; describing an event in the email text is not sufficient.

There may be situations when an SAE/AESI has occurred and the investigator has minimal information to include in the initial SAE/AESI report to Croma, or their representative. However, it is very important that the investigator always makes an assessment of causality for every event prior to transmission of the SAE/AESI report form. Minimum criteria are identifiable subject (number), suspect product (i.e., IMP or concomitant medication), an identifiable reporting source (investigator/study-site identification) and an event or outcome that can be identified as serious or as an AESI. The investigator may change his/her opinion of causality in the light of follow-up information, amending the SAE/AESI report form accordingly. The causality assessment is one of the criteria used when determining regulatory reporting requirements for SAEs.

#### **14.6.2 Exposure *In Utero* during Clinical Studies**

The Sponsor or representative must be notified of any subject that becomes pregnant while participating in this clinical study. Although pregnancy is not technically an AE, all pregnancies must be followed to conclusion to determine their outcome. This

information is important for both drug safety and public health concerns. It is the responsibility of the investigator or designee to report any pregnancy in a subject that occurs during the study to [REDACTED] Clinical Research, as specified above ([Section 14.6.1](#)) **within 24 hours** of awareness of the pregnancy, using the pregnancy reporting form.

Pregnant subjects will be withdrawn from the study if pregnancy is detected at the Screening or Baseline Visit. Following detection of pregnancy, no invasive assessments may be conducted in pregnant women. The treatment code for pregnant women will be unblinded.

#### **14.6.3 Overdose**

Overdose is defined as any dose above the total body dose per injection (i.e., 20 U/treatment of either BoNT/A-DP or [REDACTED]). Single treatment doses of up to 50 U of [REDACTED], a botulinum toxin with similar potency units to the study drug, are frequently used for cosmetic/aesthetic indications, and it is generally recognized that doses greater than 20 U may be required for larger muscles. The treatment dose for both products in this study is 20 U and the treatment vials for both products contain only 50 U, hence there is virtually no risk of overdose.

#### **14.7 Urgent Safety Measures**

The investigator may take appropriate urgent safety measures in order to protect subjects against any immediate hazard to their health or safety. The measures should be taken immediately and may be taken without prior authorization from Croma. In the event of an apparent immediate hazard to the subject, the investigator will notify the Sponsor immediately by phone and confirm notification to the Sponsor in writing as soon as possible, but within one calendar day after the change is implemented. The Sponsor (Croma-Pharma GmbH) will also ensure the responsible Institutional Review Board (IRB)/Independent Ethics Committee (IEC) is notified of the urgent measures taken in such cases, according to local regulations.

#### **14.8 Pre-existing Diseases**

Pre-existing diseases that are present before entry into the study and described in the medical history and that manifest with the same severity, frequency, or duration subsequent to IMP administration, need not be recorded as AEs. However, if there is an increase in severity, frequency or duration of a pre-existing disease, the event shall be documented as an AE.

#### **14.9 Unexpected Adverse Events**

An unexpected AE is an AE whose nature, severity, specificity, or outcome is not consistent with the term, representation, or description used in the Reference Safety Information of the IB/SmPC. “Unexpected” also refers to the AEs or suspected adverse

reactions that are mentioned in the IB as occurring with a class of drugs or as anticipated from the pharmacological properties of the drug, but are not specifically mentioned as occurring with the particular drug under investigation.

Each unexpected AE experienced by a subject will be recorded on the AE eCRF.

#### **14.10 Medication and Non-Drug Therapy History**

All medication taken for up to eight weeks prior to ICF signature, and all concomitant medications taken or administered during the study, will be documented in the subject's clinic/hospital and study records using the guidelines set forth by the Sponsor. The prior and concomitant medication information will be documented on the Concomitant Medication eCRF.

In addition to product name (preferably generic name), the dose, indication, route of administration and frequency, as well as the start and end date of treatment, will be documented. In the context of this study, information on non-drug therapies will only be collected in relation to SAEs.

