### 10.2 Exclusion Criteria

Subjects who meet **ANY** of the following criteria are **NOT** eligible for this study:

- Previous treatment with any serotype of botulinum toxin for any indication within the 12 months prior to Screening, or any planned treatment with botulinum toxin of any serotype for any reason during the study (other than the investigational treatment).
- Known hypersensitivity to either study medication or its excipients.
- Any medical condition that may place the subject at increased risk due to exposure to botulinum toxin, including diagnosed myasthenia gravis, Eaton-Lambert syndrome, amyotrophic lateral sclerosis, profound atrophy or weakness in the target muscles, or any other condition (at the investigator's discretion) that might interfere with neuromuscular function or contraindicate botulinum toxin therapy.
- Facial laser or light treatment, microdermabrasion, superficial peels or retinoid therapy within the three months prior to Screening or planned during the study.
  - Apart from the procedures specified above, previous treatment with any facial aesthetic procedure in the glabellar area (including chemical peeling, injection with biodegradable fillers, photo-rejuvenation) within 12 months prior to Screening or planned during the study.
- Previous insertion of permanent material in the glabellar area, or planned insertion during the study.
- Any planned or history of surgery in the glabellar area and/or canthal line area, or scars in the glabellar and/or canthal line.
- Active skin disease/infection or irritation at the treatment area.

- Inability to substantially lessen glabellar frown lines and or lateral canthal lines even by physically spreading them apart.
- Use of a muscle relaxant within two weeks prior to Screening, or planned use during the study.
- Marked facial asymmetry or ptosis of eyelid and/or eyebrow, or current facial palsy or neuromuscular junction disorders as judged by the investigator.
- Pregnant, breastfeeding or planning to become pregnant during the study.
- Use of prohibited medication including anticholinergic drugs, or drugs which could interfere with neuromuscular function, including aminoglycoside antibiotics and curare-like compounds within two weeks prior to Screening or planned during the study.
- Planned surgery with general anesthetic (use of local anesthetic outside the glabellar area is permitted).

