#### **Prohibited Medication and Excluded Non-drug Therapies**

The medication listed below must not be taken during the conduct of the study:

- Treatment with botulinum toxin of any serotype for any reason during the study, other than BoNT/A-DP or [REDACTED] administered as part of this study.
- Use of a muscle relaxant.
- Use of anticholinergic drugs, or drugs which could interfere with neuromuscular function, including aminoglycoside antibiotics and curare-like compounds.
- Surgery with general anesthetic.

The following non-drug therapies are excluded during the study:

- Facial laser or light treatment, microdermabrasion, superficial peels or retinoid therapy.
- Treatment with any facial aesthetic procedure in the glabellar area (including chemical peeling, injection with biodegradable fillers).
- Insertion of permanent material in the glabellar area.
- Surgery in the glabellar area including surgical removal of the *corrugator*, *procerus* or *depressor supercilii* muscles or a combination of these.

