### **15.4.3 Further Analyses**

Baseline data, including demographic data, will be analysed descriptively. Subject disposition, including discontinuation and reasons for discontinuation, and subject exposure will be tabulated in detail. Concomitant medication, including application site concomitant medication, will be coded according to the World Health Organization (WHO) drug dictionary and tabulated accordingly.

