## 8.3 Protocol Deviations

The number of subjects excluded from SAF, and FAS populations and reasons for exclusion will be summarized by treatment group and overall.

Analysis set membership details will be listed, including reason for exclusion from each analysis set.

All major protocol deviations identified will be summarized by treatment group and overall. Minor protocol deviations will be listed only.

A listing will include the inclusion/exclusion criteria violated at Screening and at the Baseline visit as well as other protocol deviations identified based on data recorded on the electronic CRF (eCRF) and/or protocol deviation logs from [REDACTED] (based on All Subjects).

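### Excluded cosmetic procedures are not systematically collected after Baseline, which leaves the Week 8–16 responder and duration-of-effect endpoints open to undated co-treatment

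*Protocol*

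**What the plan says.** Under Prohibited Medication and Excluded Non-drug Therapies, which belongs to section 14.10, the protocol states: "The following non-drug therapies are excluded during the study". The list has four entries. The first is "Facial laser or light treatment, microdermabrasion, superficial peels or retinoid therapy". The second is "Treatment with any facial aesthetic procedure in the glabellar area (including chemical peeling, injection with biodegradable fillers". The third is insertion of permanent material in the glabella. The fourth begins "Surgery in the glabellar area including surgical removal of the" and goes on to name the muscles.

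The preceding text of 14.10 requires all concomitant medications to be documented, with route and dates. For the other category it says that "information on non-drug therapies will only be collected in relation to SAEs".

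The schedules in Protocol 4.1 and Table 12-1 collect concomitant medication and adverse events at every post-Baseline visit. Neither has an item for procedures or non-drug therapies.

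On the analysis side, SAP 8.3 lists "other protocol deviations identified based on data recorded on the electronic CRF (eCRF) and/or protocol deviation logs". It summarises major deviations by arm and only lists minor ones. SAP 6.3 names four deviations as major in advance, and use of an excluded therapy is not one of them.

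**The concern.** The protocol imposes a restriction and, in the same section, limits collection of the information needed to check it. A glabellar filler or peel given during follow-up is normally unrelated to any SAE, so a site following 14.10 as written has no instruction to record it.

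Every responder, onset and duration endpoint rests on a 0–3 severity score of the treated lines. The sponsor considered these treatments relevant enough to exclude them both at entry and during the study. Subjects whose effect is fading have the most reason to seek one. Protocol 7.1 puts recovery of nerve function at about two to three months, which falls inside the Week 8–16 visits. If one product wore off sooner, its subjects might use more procedures, and a real difference in duration would be understated. Without dates, no analysis can separate assessments made before a procedure from those made after it.

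**Working it through.** **Is there another planned route to the information?**

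| Possible route | What the plan provides | Does it capture an excluded procedure? |
|---|---|---|
| Non-drug therapy data (Protocol 14.10) | Collected only if linked to an SAE | Rarely |
| Concomitant Medication form (14.10) | All medications, asked at each visit | Possibly retinoids; not laser, fillers or surgery as such |
| Visit schedule (4.1, Table 12-1) | Medication, AE and AESI items | No item |
| Compliance monitoring (12.7; SAP 8.5.2) | No separate procedure, because study procedures are supervised on site | No; cosmetic procedures happen elsewhere |
| Mandatory termination (9.7) | Another investigational product or another botulinum toxin | No |
| Deviation listing (SAP 8.3) and blinded data review (SAP 6.4) | eCRF data and/or deviation logs | Only if the site happens to learn of it |

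Only the last route is open to all the listed procedures, and nothing prompts it.

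**How a procedure could enter duration of effect.** SAP 8.6.3 counts loss for a Week 4 responder when the maximum-frown score returns to that subject's Baseline grade or worse. Duration is the date of loss minus the injection date, plus 1. Responders who keep their response are censored at the last visit with a score. Take a hypothetical subject with Baseline 3 and Week 4 score 1 who would return to 3 at Week 12.

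- Without a procedure: event on day 12 × 7 + 1 = 85.
- With a procedure at about Week 10 that holds the score at 2 through Week 16: no event, censored on day 16 × 7 + 1 = 113.

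One point on the scale removes the event. The same subject, at score 2, is still not a responder at Weeks 12 and 16, because response requires 0 or 1. Duration is therefore the more sensitive endpoint.

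**Scale of a shift in a responder rate.** The plan's only precision figure comes first (Protocol 15.1; SAP 5: 100 per group, 81.5% in both):

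1.96 × √(2 × 0.815 × 0.185 / 100) = 0.1076, which reproduces the stated 10.8 points.

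The documents give no rate of use. Suppose a fraction f of one arm has an excluded therapy and every non-responder among them becomes a responder. The rate rises by f × (1 − p), where p is the response rate the users would have had anyway.

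- f = 1%: 0.01 × 0.185 = 0.2 points if p = 81.5%; 1 point if p = 0.
- f = 10%: 0.10 × 0.185 = 1.9 points if p = 81.5%; 10 points if p = 0.

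Both f and the complete conversion are assumptions, chosen to show a range. The 10.8 points describe Week 4 at the expected 81.5% rate, so they are not a direct yardstick for Weeks 8–16.

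**The case against.** The strongest reply is that limiting one data category does not suspend deviation documentation. Use of an excluded therapy is a protocol deviation, and SAP 6.4 and 8.3 provide for review and listing. The eCRF, monitoring plan and sponsor guidelines are not among the documents and may prompt the question. This stands in part: a reader might infer that such use is never recorded, and the documents do not support that. They support only that it is not systematically collected.

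Other limits also stand.

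- **Retinoids.** They are listed as non-drug but are ordinarily medication, so they may reach the Concomitant Medication form. The protocol leaves this unclear.
- **Causal premise.** Protocol 7.2 says most rejuvenation procedures leave the responsible musculature untouched, and the main score is taken at maximum frown. The documents do not show that each listed therapy changes that score.
- **Use of the data.** The study is randomised, double-blind and descriptive. Efficacy uses the FAS as randomised with no per-protocol set, so the main estimates would not change. Randomisation and blinding do not, however, prevent use from differing between arms if the products wear off at different times.

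Two further inferences should be resisted.

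- **Look-back.** The eight-week medication history is shorter than the exclusion windows, for example "previous treatment with any facial aesthetic procedure in the glabellar area (including chemical peeling, injection with biodegradable fillers, photo-rejuvenation) within 12 months" in Protocol 10.2. But that history is a separate record. Eligibility is checked at Screening, and violations of the criteria are listed under SAP 8.3.
- **Application-site table.** Protocol 15.4.3 says "Concomitant medication, including application site concomitant medication, will be coded" and tabulated. It promises no separate table, and SAP 8.4.4 tabulates prior and concomitant medications as a whole.

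**Conclusion.** The point holds in a limited form. After Baseline, use of the excluded procedures has no planned systematic collection and can be found only ad hoc. The endpoints mainly exposed are the Week 8, 12 and 16 responder rates and duration of effect, and duration is named in the study title.

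A reader might infer a threat to the Week 4 co-primary endpoints. A procedure after Week 4 cannot affect them, and the motive of a fading effect points to later visits. Exposure before Week 4 is possible but less likely.

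The size cannot be estimated from the documents and may be small. The range in the working rests on assumed use of 1–10% in one arm and conversion of every non-responder among the users; it is not a forecast. This is an inexpensive improvement to data that cannot be reliably reconstructed later. It does not invalidate the trial.

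**What to change.** 1. **Protocol 14.10.** Require that use of any therapy on the excluded list be asked about at each of the six existing post-Baseline visits and recorded on the eCRF with type, facial area and date. Other non-drug therapies can stay limited to SAEs. Add the item to Protocol 4.1 and Table 12-1.
2. **Retinoids.** State that they are recorded on the Concomitant Medication form.
3. **SAP 6.3, 8.3 and 8.4.4.** State how such use is classified as a deviation, and list and tabulate it by arm.
4. **SAP 8.6.3.** Add a sensitivity analysis that censors duration of effect at the last assessment before such use and excludes later assessments from the Week 8, 12 and 16 responder analyses. Such censoring may be informative, since use may follow a fading effect, so it should be read beside the main analysis.

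The cost is one eCRF log, one question per existing visit and one sensitivity analysis. No visit is added.

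SAP version 2.0 is dated 20 January 2021, and the protocol anticipated primary completion in October 2020. If follow-up has already ended, tabulate the logged cases by arm and state the limitation in the clinical study report.
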